Due to the problem of attrition in the control group, it has been suggested in the last International Myopia Conference that controlled field studies be performed by a virtual group, without performing a non-inferiority study, since atropine 0.01% could not be taken as gold standard because it is not yet approved and as we said, it is off-label in Argentina. Data on progression in Asia or Europe could be used for this virtual control group, but it would be more convenient to have a virtual control group in one's own living environment. In the case of our country there is already a possible control group of 114 children of 12 years of age on average who were followed up with cycloplegia during the years pre-pandemic and from which it is known that the progression was from 0.43+/-0.52 diopters in one year.³⁶

It is thus proposed to perform a prospective clinical study in 100 children who will be enrolled when in the usual consultation for their eyeglasses control they can choose to do the treatment accessible in our environment (the diluted atropine drop) or a treatment that is possibly equally effective with special glasses designed in our environment. It is

expected that there will be similarity of effect on progression because the lens is based on the principles of defocusing of eyeglasses and contact lenses already proven by the international industry.³⁷ Our lens has the characteristic of being much simpler in its carving and construction, making it more economical for our environment where it has already been presented from the theoretical point of view.³⁸

Moreover, the special myopia control spectacle lacks the possible toxic effects of a drop instilled in the eye for many years until emerging adulthood. In addition, to avoid including children who may have rapid progressions to high myopia, treatment will be offered only to children over 8 years of age. In our environment, where children are outdoors a lot, the progression is slower than in Asian countries and is around -0.50 diopters per year, as we said.³⁶ A strong myopia is the one that exceeds -5.00 diopters.³⁹ Thus the risk for a child included in this project is to progress -0.25 diopters in six months (the resolution limit of the measurement method), so each child who does not respond well with arrest of progression at six months may be removed from the protocol and switched to atropine treatment.

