Given the above-mentioned background, the following study has been designed to evaluate the arrest of myopia progression with the daily use of nationally designed glasses, comparing such progression with a virtual control group of similar age in a population of myopic children and adolescents of the same environment in our country.

WORKING HYPOTHESIS

The nationally designed lenses can be as effective as the proven international industry designs that have been subjected to controlled trials against natural history of the disease.

PURPOSE

To treat a group of consecutive volunteer patients who choose between the affordable treatment in our environment (daily diluted atropine drops for several years) or the special lenses for myopia control designed by the National Industry. The purpose is to compare the progression during one year with the national lenses with respect to the progression with the foreign lenses and/or with the natural history of a virtual control group.

OBJECTIVES

Primary

To assess whether the intervention with locally designed spectacles is well tolerated and adhered to with daily use in childhood and adolescence.

Secondarily

To assess whether intervention with locally designed glasses can control myopia progression in childhood and adolescence.

DEFOCUS GLASSES OF NATIONAL DESIGN

The design of the national defocus lens is based on the original design presented by Carly Lam,⁴⁰ with a 9 mm central zone for distance correction and a correction ring with a +3.50 dioptre defocus between 9 and 32 mm in diameter to act in principle on the para foveal zone which is the one that detects the defocus that governs the growth of the eye.⁴¹ Instead of peripheral defocusing micro lenses that do not alter the visual field in the area of the 32

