All the data of affiliation, contact telephone number, date of birth, refraction under cycloplegia, axillary length and questionnaire will be entered in a centralized digital history by NOVAR developers. These data will be kept confidential. During follow-up visits, accredited professionals throughout the country will have access to upload the data required for each visit. One month after the eyeglasses are delivered, the professional will conduct a telephone survey to parents to evaluate adherence. The first stage of the study will be completed after one year and the child will be able to continue with the treatment for myopia control according to the consensus guidelines on myopia treatment of the Myopia Study Group of the SAOI (Annex I). For virtual control group, data will be taken from 114 children followed with cycloplegia by the pandemic study group during the years 2018-2019 that showed for an average age of 12 years an annual pre-pandemic progression of -0.45 D. In the present study, We expect to evaluate the progression with peripheral defocus treatment over one year of an equivalent group of children.

WORK PLANNING / GANTT CHART:

Activity	TIME IN MONTHS						
	1	2-4	5-24	25	26	27	28
Project Design	X	X					
Bibliographic search	X			X	X		
Ethics Committee Presentation		X					
Data collection			X				
Data analysis				X	X		
Preliminary results					X	X	
Final Results						X	X
Report writing							X

INCLUSION / EXCLUSION CRITERIA

All consecutive patients of both genders who freely opt for lenses of national industry will be included in the present study. All patients who present any systemic or ocular pathology that may affect their refraction measurements or their evolution will be excluded from the study. Also excluded from the protocol in the follow-up will be those patients who, even using defocus glasses, had in 6 months an improvement equal to that expected without any intervention. These patients will be treated with other options available in our environment at the time of the change. The computerized medical records system will be configured to detect such patients at the time of loading the follow-up data and will send an alert to the investigators.

EVALUATION OF TOLERANCE AND ADHERENCE

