Adherence will be evaluated at the one-year follow-up and will be reported as the number of cases that failed to complete the three scheduled visits in one year with respect to the total number of cases that were enrolled in compliance with the first visit and the delivery of the spectacle. Tolerance of these glasses will be assessed with a tolerance questionnaire that is presented in the attached medical record. This questionnaire has already been tested on 24 subjects aged 18 to 24 years in a pilot trial presented at the International Myopia Conference, as explained in the previous section on the defocus spectacle, showing good tolerance in these subjects. Some tests in younger children that were performed in the last months show that tolerance is very good in them, since minors have greater plasticity and adaptability than young adults previously tested. Tolerance and adherence will be classified as GOOD / BAD, in a dichotomous way, with the cut-off according to the answer given by whether the child tolerated them well or not. On the other hand, tolerance will also be evaluated in dichotomous form with responses to reading and walking

performance.

PROCEDURES TO GUARANTEE ETHICAL ASPECTS

The anonymity of all participants will be preserved. Patients' names will be removed from the database for statistical analysis. The only ones who will know the names of the patients are the physicians involved in their primary care, and they will have to keep the information in their respective institutional medical records and enter the data necessary for the research in a web form designed by the sponsoring company.

The Declaration of Helsinki and its modifications, the Good Clinical Practices guide, the harmonization norms and the resolution of the Ministry of Health 1480/11 will be observed and taken into account as guidelines (See informed consent ANNEX VI). It is stated for the record that the principal investigator does not have any type of conflict of interest since the patenting of the defocus glasses is the responsibility of the sponsor's company.

SAFETY PRECAUTIONS

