It is considered necessary for the development of the study the free coverage by the sponsors (NOVAR) of the peripheral defocus glasses. Money will also be spent for the web form system programmers and for the two ophthalmologists in charge of the study.

The expenses of the medical consultations made by the subjects at the time of enrollment and follow-up will be paid by the medical system of each of the accredited institutions (whether these are social security or prepaid health insurance of the subjects) since no more consultations are required for the study than the three per year recommended for myopia control according to the last consensus of the Myopia Study Group of the SAOI (Annexed). No corneal or eyeball complications are expected (as with contact lenses or drops) since the glasses are a prosthesis that is not introduced into the body and acts at a distance.

CENTERS OF ATTENTION

Eight enrollment centers will be chosen. To avoid biases in the methodology and to adjust the feasibility of developing a joint protocol, training interviews will be conducted with the investigators from each center in a timely manner. The principal investigator will maintain weekly communication by telephone with each of the investigators involved in each center.

ENROLLMENT

Consecutive patients attending the above-mentioned care centres for glasses prescription will be enrolled. Family members will be informed in writing and verbally of the objectives of the study and will sign an informed consent for the study.

Subjects must be willing to participate in a study lasting 1(one) year (it will be explained to them at the beginning of the study that the free treatment materials will in principle only extend for that period).

Risks, discomforts or ethical issues related to participation:

Clinical and biometric ophthalmological studies with or without cycloplegia are routine and free of discomfort for patients.

CRITERIA FOR INCLUSION

- Patients of both sexes aged between 8 and 16 years, without ocular pathology added to myopia.

- Myopia ranges between 2.00 D and 5.00 D in both eyes.
- Refractive astigmatism less than one diopter in each eye.
- Visual acuity 20/25 or better in both eyes.

EXCLUSION AND ELIMINATION CRITERIA

Patients who do not meet the aforementioned inclusion criteria.

Patients with poor adherence to treatment demonstrated by poor compliance with follow-up interviews.

Patients whose family members do not sign the informed consent form.

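### The one-year adherence figure counts children removed at six months for progression as non-adherent, so it depends partly on lens efficacy and on how removal is applied

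*Combined protocol and SAP*

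**What the plan says.** The primary objective (Objectives) is to find out whether the intervention "is well tolerated and adhered to with daily use in childhood and adolescence".

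Evaluation of Tolerance and Adherence gives the one-year measure. Adherence is reported as "the number of cases that failed to complete the three scheduled visits in one year with respect to the total number of cases", the denominator in full being "the total number of cases that were enrolled in compliance with the first visit and the delivery of the spectacle". No reason for non-completion is set apart.

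Inclusion / Exclusion Criteria contains the six-month rule: "Also excluded from the protocol in the follow-up will be those patients who, even using defocus glasses, had in 6 months an improvement" no better than that expected untreated. These children then receive other treatment.

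Two other places describe the same situation in softer terms. Current State of Research says a child who does not respond at six months "may be removed from the protocol and switched to atropine treatment". Human Resources describes an automatic report when progression exceeds 0.25 D in six months, so that the researchers can take precautions.

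On the case record form, the second visit is at six months (Part III) and the third at twelve months (Part IV). The days per week on which the glasses are not used are asked at month 1 (Part II BIS) and month 6 (Part III BIS). Part IV, as shown, has no questionnaire.

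**The concern.** The removal rule acts at month 6 on refraction, and the adherence measure looks at attendance up to month 12. A child who wears the glasses every day and attends every visit, but progresses, leaves the protocol after the second visit. That child stays in the denominator and enters the count of failures. No passage separates such a child from one who stopped coming.

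With the same wear, a less effective lens would show worse adherence. A poor one-year figure could mean that children did not keep to the glasses, or that they did and their myopia progressed. A reader of the report could not tell which.

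**Working it through.** **Structure (no assumptions).** Four statements, side by side:

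1. Failure means not completing all three visits within the year, for any reason.
2. The denominator is everyone with a first visit and delivered spectacles, so removed children remain in it.
3. Removal for progression happens at six months and expressly covers children who use the lens.
4. The third visit is at twelve months.

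From 3 and 4, a removed child cannot complete the third visit within the protocol. From 1 and 2, that child is counted as an adherence failure.

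**The plan's own figure.** The documents give no adherence target. The planning inputs that bear on the size are in Sample and Sample Size: a difference of 0.25 D, SD 0.50 D, n = 31, and 38 after 20% loss. A one-sample normal formula, assuming two-sided 5% and 80% power, gives (0.50 × (1.960 + 0.842) / 0.25)² = 31.4, in line with 31. Then 31 × 1.2 = 37.2, rounded up to 38.

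**Inputs for the size.**
- Untreated progression: 0.45 D/year (Methods). Current State of Research gives 0.43 ± 0.52.
- Lens effect: 0.25 D/year, taken from the sample-size paragraph.
- Six-month SD: not in the documents. Assumed between 0.50/2 = 0.25 D and 0.50/√2 = 0.354 D.
- Threshold: the removal rule gives no dioptre value. Half the untreated rate is 0.45/2 = 0.225 D, and the alert is at 0.25 D, so both are used.
- Every child over the threshold is removed. All children wear the lens and attend until then. Change is normal.

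**Continuous scale, lens works as planned.** Six-month mean = (0.45 − 0.25)/2 = 0.10 D. Proportion removed = 1 − Φ((threshold − 0.10)/SD).

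| Threshold | SD 0.25 | SD 0.354 |
|---|---|---|
| 0.25 D | z = 0.60, 27.4% | z = 0.42, 33.6% |
| 0.225 D | z = 0.50, 30.9% | z = 0.35, 36.2% |

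The range is 27–36%, or about 14 to 18 of 50 children.

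**Continuous scale, no lens effect.** Mean 0.225 D. At 0.25 D, z = 0.10 and 0.07 give 46.0% and 47.2%. At 0.225 D, the result is 50%. The range is 46–50%, or 23 to 25 of 50.

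**Refraction read in 0.25 D steps, lens works as planned.** The protocol calls 0.25 D the resolution limit of the measurement.
- If removal needs a 0.50 D reading (true change above 0.375 D): z = 0.275/0.25 = 1.10 gives 13.6%, and z = 0.275/0.354 = 0.78 gives 21.8%.
- If a 0.25 D reading is enough (true change above 0.125 D): z = 0.025/0.25 = 0.10 gives 46.0%, and z = 0.025/0.354 = 0.07 gives 47.2%.

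The range is about 14–47%, or roughly 7 to 24 of 50.

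**Sensitivity.** With 0.43 D/year, SD 0.26 to 0.37 D (0.52/2 and 0.52/√2), a 0.25 D threshold and a continuous scale, a lens that halves progression gives 29–35%. A lens with no effect gives 45–46%.

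**The case against.** Several points on the other side are sound.

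- **Removal may not be automatic.** Only Inclusion / Exclusion Criteria reads as mandatory. Elsewhere removal is permitted, or there is only an alert. This stands: it decides how many children are affected, though not how a removed child is counted.
- **There is other adherence information.** The month-1 and month-6 questionnaires ask about wear at home and days not used, and tolerance is assessed by questionnaire. All of this is collected by the six-month visit, so removal does not touch it. A reader might infer that the trial cannot show whether children keep to daily use. The documents do not support that. The gap is that the one-year definition uses none of the wear items, and the good/bad classification is cut on the tolerance answer.
- **Removed children are not all faithful wearers.** A child who rarely wears the lens may also progress and be removed. This stands, so the percentages are an upper scenario for misclassified wearers.
- **Removed children may still attend.** The three yearly visits are described as usual care. But these children are outside the protocol, and nothing says that their later visits count.

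A second tempting reading concerns the elimination criterion "Patients with poor adherence to treatment demonstrated by poor compliance with follow-up interviews". One might infer that it drops true non-adherers from the denominator and inflates adherence. The text does not support this. The denominator is fixed at enrolment and spectacle delivery, and a child eliminated for missed follow-up also fails the three-visit test and so already counts as a failure.

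**Conclusion.** The point holds in a limited form. Each child actually removed for progression is counted as non-adherent at one year, whether or not the lens was worn. That follows from the wording alone. The figure therefore depends partly on lens efficacy and on how removal is applied. It is not a pure readout of efficacy, because ordinary missed visits enter it too, and the tolerance half of the primary objective does not use it.

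The size rests on mandatory removal, normality and an assumed six-month SD. A reader might take 64–73% (100 minus 36 and 27) as a ceiling on measurable adherence. It is not one: removal may be optional, and reading in 0.25 D steps widens the range in both directions. The continuous-scale results exceed the 20% loss allowed for in the sample size. The stepped results lie on both sides of it.

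**What to change.** - In Evaluation of Tolerance and Adherence, report children removed for progression as their own category, separate from missed visits. Keep the denominator as it stands. Children eliminated for poor follow-up need no new rule.
- Beside the one-year figure, report wear at six months in all children who attend that visit, removed or retained. Use the days-not-worn item on Part III BIS, with the same measure for all.
- Reconcile Current State of Research, Inclusion / Exclusion Criteria and Human Resources on whether removal is mandatory, optional or only an alert, so that a removed child is defined. Which rule applies is a clinical matter for the investigators.

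The cost is wording in these sections and one extra table, with no new data. The limits are small: removed children contribute only six months of adherence observation, and the form as shown offers no wear measure at month 12.

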mm diameter ring with the treatment,⁴⁰ the national design that was presented has a uniform +3.50 diopter power zone that alters the visual field by 5% at 10 degrees from the circular shaped fovea,³⁸ as presented at the International Myopia Conference a month ago. As it is known that positive defocus in 30-40 minutes of exposure modifies the axial length (measured with Lenstar) by 10 microns due to changes in the choroidal thickness,⁴² The national design has been tested on 17 volunteer subjects showing a significant change of 11 microns in the axial length of their eyes, suggesting this pilot study (in the process of being published) that the lenses should be effective in halting the progression of myopia, as changes in the choroid are the first event in the retinal message that governs ocular growth.⁴³ This, coupled with the survey that gave a good reading tolerance in 70% of the 17 respondents within a month of wearing them, was presented at the Conference and is in the public domain. Respondents found it difficult to walk around with these lenses because they are like an executive bifocal, but tolerated them well for reading at home, with small lateral movements of the head when reading A4 texts or the computer. It is therefore our intention to do a free field test with such lenses on a larger sample.

POPULATION

Consecutive patients between 8 and 16 years of age who attend the institutions accredited for this study. These institutions will be accredited only if they can perform routine studies for myopia control (refraction exam and optical biometry).

USE OF GLASSES

Once the eyeglass prescription has been written by the ophthalmologist, the enrolled patients will be seen in opticians accredited for this study in close proximity to the

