ophthalmology offices that are members of the research team. The opticians and ophthalmologists will be asked to watch a video on myopia control developed by the principal investigators where this treatment methodology is explained during the evaluation process at the center of care. The opticians will verify the optical centration in the frames chosen ad hoc, with a modern digital centration system provided by the sponsors. After 15 days, when the glasses with the correct centering are ready, the subjects will go to the optician's office to try on the glasses in that room. On this occasion, as always in these cases, the optician will evaluate the subject's adaptation and mobility in the optician's shop, instructing the child to wear the glasses at home for a couple of days and then to wear them for as long as possible.

SAMPLE AND SAMPLE SIZE

The sample size will be 50 subjects of both genders to compare with the studies abroad that consist of an n between 40 and 90 subjects and the natural history in our country that counted 114 subjects. There will be a group of subjects who will be treated with the nationally designed defocus glasses. Statistical calculation for a difference of 0.25 diopters in progression with respect to controls, for a standard deviation of 0.50 diopters gives an $n = 31$ subjects and taking into account a 20% loss to follow-up the n should equal 38 subjects in the group. Thus reaching 50 subjects exceeds expectations.

METHODS

This field study to test tolerance and percentage of effectiveness of defocus lenses in the control of myopia will include boys and girls from 8 to 15 years of age who voluntarily

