Do you take tutoring outside of school? (Circle) YES NO

How many hours do you spend outdoors when you leave school?Hs

How many hours per day do you spend reading books or doing homework?
.....Hs

How much time per day do you spend playing with your cell phone or tablet?
.....Hs

ON ANY SATURDAY OR SUNDAY.....

How many hours per day do you spend reading books or doing homework?Hs

How many hours per day do you spend outdoors on a weekend day?Hs

How much time per day do you spend playing with your cell phone or tablet?
.....Hs

PART II EYEGLASS DELIVERY

DATE

PART II. BIS (ATTACHMENT QUESTIONNAIRE)
AT THE MONTH OF DEFOCUS EYEWEAR DELIVERY (TELEPHONE SURVEY)
DATE

Have you worn the glasses at home during this month? YES NO

Have you worn glasses all day this month? YES NO

If you answered "YES" to any of the above, continue with these

In general, do you tolerate them well? YES NO

Have you ever had trouble turning your head to look sideways? YES NO

Out of the seven days of the week, how many days do you not use them?.....

Have you ever had trouble turning your head to look down when reading? YES NO

Have you ever had trouble turning your head to look down when walking? YES NO

PART III

DATE SECOND VISIT AFTER SIX MONTHS.....

EYE DER SPHERICALCILINDRICAL AXIS.....

SPHERIC IZQ EYE.....CILINDRITRIC AXIS.....

AXIAL LENGTH OD..... OI.....

PART III (BIS) SIX MONTH ADHERENCE QUESTIONNAIRE

Have you worn your glasses at home during this month? YES NO

Have you worn glasses all day during this month? YES NO

If you answered "YES" to any of the above continue with these.....

In general, do you tolerate them well?

YES NO

Have you found it difficult to turn your head to look sideways? YES NO

Of the seven days of the week, how many days do you not use them?

Did you have trouble turning your head to look down when reading? YES NO

Have you had trouble turning your head to look down when walking? YES NO

PART IV

DATE THIRD VISIT AT TWELVE MONTHS.....

RIGHT EYE SPHERICALCILINDRICAL AXIS.....

LEFT EYE SPHERICAL.....CYLINDRICALAXIS.....

AXIAL LENGTH OD..... OI.....

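### An enrolled child who tries the glasses at the optician and does not take them enters neither primary result, so any such refusals would flatter adherence and tolerance

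*Combined protocol and SAP*

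**What the plan says.** The primary objective (OBJECTIVES) is "To assess whether the intervention with locally designed spectacles is well tolerated and adhered to with daily use in childhood and adolescence".

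The order of events is set out in three places:

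- **Enrolment comes first.** Under ENROLLMENT, patients are enrolled and consent is signed at the care centres. Under USE OF GLASSES, "the enrolled patients will be seen in opticians accredited for this study in close proximity to the" ophthalmology offices, so they are already in the study when they reach the optician.
- **Then the try-on.** About 15 days later, when the glasses are ready, "the subjects will go to the optician's office to try on the glasses in that room". There, "the optician will evaluate the subject's adaptation and mobility in the optician's shop", and the child is told how to start wearing them at home.
- **Then measurement.** Under METHODS, "One month after the eyeglasses are delivered, the professional will conduct a telephone survey to parents to evaluate adherence". SAFETY PRECAUTIONS times the tolerance call in the same way. The record form repeats the questionnaire at six months.

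Under EVALUATION OF TOLERANCE AND ADHERENCE, adherence is "reported as the number of cases that failed to complete the three scheduled visits in one year", taken "with respect to the total number of cases that were enrolled in compliance with the first visit and the delivery of the spectacle". Tolerance is scored GOOD or BAD from the questionnaire, with reading and walking also scored as two-way results.

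On the record form, the page headed "PART II EYEGLASS DELIVERY" shows a date and nothing else.

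**The concern.** Delivery is a condition for entering the adherence denominator, and it is also the starting point for both tolerance questionnaires. Between enrolment and delivery comes the child's first contact with the lens. A child who puts the glasses on, dislikes them and does not take them has given an answer to the primary question, yet no section counts that answer. The form has no field to show that it happened or why.

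The omission can act in one direction only. A refusal at first wear is an unfavourable outcome, and leaving it out can only make the glasses look better tolerated and better adhered to. The plan also gives reason to expect some difficulty: under DEFOCUS GLASSES OF NATIONAL DESIGN it reports that pilot users had trouble walking in these lenses and that 70% of 17 had good reading tolerance. The optician's check is the only direct professional observation of mobility that the plan describes, and the form does not keep it.

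**Working it through.** **The plan's own figures.** The plan states no expected adherence or tolerance rate and no expected number of refusals. Its one calculation, under SAMPLE AND SAMPLE SIZE, concerns progression. It reproduces as (0.50 × (1.96 + 0.84) / 0.25)² = 31.4 against the stated 31, with 80% power and a two-sided 5% level assumed, and 31 × 1.20 = 37.2, rounded up to the stated 38. It has no bearing on this point.

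**Inputs.**

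- E = 50 enrolled (SAMPLE AND SAMPLE SIZE).
- k = enrolled children who try the glasses and do not take them. Not given, so varied from 0 to 10.
- a = favourable rate among delivered children. Not given. For illustration: 80% for adherence, the complement of the planned 20% loss to follow-up, and 70% for tolerance, the pilot figure for reading.
- Adherence failures are taken as a subset of the denominator, as a proportion requires. Every delivered child is assumed to answer the tolerance item, and no glasses are assumed undelivered for logistic reasons.

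**Formula.** Rate among delivered children = a. Rate among all enrolled = a × (E − k)/E = a × (1 − k/E). Overstatement = a × k/E.

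The plan prints the failure fraction f = 1 − a. Over all enrolled, failures are f × (1 − k/E) + k/E, so the printed fraction is too low by (1 − f) × k/E = a × k/E, the same amount with the opposite sign.

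**Results for E = 50.**

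- k = 0: no change.
- k = 1: 0.80 × 1/50 = 1.6 points for adherence; 0.70 × 1/50 = 1.4 points for tolerance.
- k = 2: 3.2 and 2.8 points.
- k = 5: 8 and 7 points.
- k = 10: 16 and 14 points.

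In whole children:

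| k | Failures / delivered | Failures / 50 | Completers / delivered | Completers / 50 | GOOD / delivered | GOOD / 50 |
|---|---|---|---|---|---|---|
| 0 | 10/50 = 20.0% | 10/50 = 20.0% | 40/50 = 80.0% | 40/50 = 80.0% | 35/50 = 70.0% | 35/50 = 70.0% |
| 1 | 10/49 = 20.4% | 11/50 = 22.0% | 39/49 = 79.6% | 39/50 = 78.0% | 34/49 = 69.4% | 34/50 = 68.0% |
| 3 | 9/47 = 19.1% | 12/50 = 24.0% | 38/47 = 80.9% | 38/50 = 76.0% | 33/47 = 70.2% | 33/50 = 66.0% |
| 5 | 9/45 = 20.0% | 14/50 = 28.0% | 36/45 = 80.0% | 36/50 = 72.0% | 31/45 = 68.9% | 31/50 = 62.0% |
| 10 | 8/40 = 20.0% | 18/50 = 36.0% | 32/40 = 80.0% | 32/50 = 64.0% | 28/40 = 70.0% | 28/50 = 56.0% |

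The section on the current state of research speaks of 100 children instead of 50. With E = 100 the effect per refusing child is halved, to 0.7 to 0.8 points.

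**The case against.** The try-on is not written as a test that a child must pass. No section withholds the glasses from a child who adapts poorly, and USE OF GLASSES reads naturally as a try-on and hand-over in one visit. A reader might infer that every child who cannot adapt in the shop drops out of the results. The documents do not support that: such a child who takes the glasses home is in the adherence denominator, is due the one-month call and is due the six-month questionnaire. This stands, and it confines the point to children who never take delivery.

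Mobility is not otherwise ignored. The questionnaires ask about looking sideways and about looking down when walking, and walking is a stated tolerance result. Home use after five in the afternoon is the intended use, so behaviour in a shop is an imperfect guide. This stands too, but the questionnaires do not reach a child who left before delivery.

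Refusals may be few. Families choose the glasses freely and receive them free of charge, and the pilot description mentions no refusal at try-on. So k may be 0, and any range must start there.

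A denominator of children who received the device is openly stated and is a legitimate quantity. It is worth keeping as a secondary result. It does not fit well as the only result when the objective is tolerance and the first wear comes before counting starts.

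Other losses could matter more. A child answering NO to both wearing questions skips the tolerance item. Elimination for poor follow-up compliance and the six-month exclusion also act on delivered children. These are separate problems that this change does not resolve.

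**Conclusion.** The point holds in a limited form. An enrolled child who tries the glasses and does not take them enters neither primary result, and the form would not show why. If there are such children, the printed adherence failure fraction is too low, and the implied adherence and the GOOD tolerance rate are too high, each by a × k/E. With 50 enrolled and rates of 70% to 80%, that is 1.4 to 1.6 points per child and 7 to 8 points for five children.

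A reader might go further and conclude that the rates are overstated as a matter of fact, or that the printed adherence figure is too high. Neither follows. The documents give no value of k and allow zero, and the printed figure is a failure fraction, so its error would be downwards. The sizes rest on assumed values of k, on the two illustrative rates and on 50 enrolled. The direction, in favour of the glasses, does not depend on them.

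This is a cheap improvement to a primary result whose possible bias has a known direction and an unknown size.

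**What to change.** In EVALUATION OF TOLERANCE AND ADHERENCE:

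- Define the primary denominator for both results as all consented, enrolled children for whom glasses were ordered.
- Count refusal of the glasses at try-on as non-adherent and as BAD tolerance.
- List non-delivery for logistic reasons separately, so that a supply failure is not read as a refusal, and say in advance how those children enter the rates.
- Report the per-delivery rates as a secondary line.

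On Part II of the record form, add delivered YES/NO with the reason if not, and the optician's adaptation and mobility observations. Use the observations descriptively: poor adaptation at try-on without refusal should not by itself count as BAD, because that child goes on to the questionnaires.

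The cost is a few sentences and a few form fields, using an assessment the optician already makes. No visit or treatment changes. The reported rates may come out slightly less favourable. If no child refuses, they are unchanged and the report can show it.
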